## LIST OF ABBREVIATIONS

Abbreviation	Term
AE	adverse event
ALT	alanine aminotransferase
ARDS	acute respiratory distress syndrome
AST	aspartate aminotransferase
ATC	Anatomical Therapeutic Chemical Classification System
BID	twice daily
BMI	body mass index
COVID-19	coronavirus disease 2019
CRF	case report form
CRP	C-reactive protein
CTCAE	Common Terminology Criteria for Adverse Events
DMC	Data Monitoring Committee
ECMO	extracorporeal membrane oxygenation
eCRF	electronic case report form
FiO 2	percentage of inspired oxygen
ICU	intensive care unit
ITT	intent to treat
LDA	longitudinal data analysis
MedDRA	Medical Dictionary for Regulatory Activities
NCI	National Cancer Institute
PaO 2	partial pressure of arterial oxygen
PLB	placebo
PP	per protocol
PT	preferred term
SAP	Statistical Analysis Plan
SARS-CoV-2	severe acute respiratory syndrome coronavirus 2
SOC	system organ class
SoC	standard of care
SOFA	sequential organ failure assessment
TEAE	treatment-emergent adverse event
ULN	upper limit of normal
WHO	World Health Organization

## 1. INTRODUCTION

This is a randomized, double-blind, placebo-controlled, 29-day, multicenter study to assess the efficacy and safety of ruxolitinib 5 mg BID + SoC therapy and 15 mg BID + SoC therapy compared with placebo + SoC therapy in participants aged  $\geq 12$  years with COVID-19-associated ARDS who require mechanical ventilation. Participants will be assigned in a 2:2:1 ratio to receive ruxolitinib 5 mg BID, 15 mg BID, or matching-image placebo for an initial period of 14 days; participants randomized to placebo will be randomized 1:1 to either receive matching placebo for 5 mg BID (1 tablet BID) or matching placebo for 15 mg BID (3 tablets BID). On Day 15, if in the opinion of the investigator the benefit/risk is appropriate, then continued treatment up to 28 days is permitted with medical monitor approval. Study treatment will be given in combination with SoC therapy according to the investigator's clinical judgment. Study treatment will be administered via an enteric feeding tube while the participant is intubated. Randomization will be stratified by ARDS severity (severe [ $\text{PaO}_2/\text{FiO}_2 \leq 100$ ] vs mild/moderate [ $\text{PaO}_2/\text{FiO}_2 > 100$  and  $\leq 300$ ]) and investigative site. Sections 2 and 5 of the Protocol provide a detailed description of the investigational product, target patient population, rationale for doses to be examined, and potential risks and benefits of treatment with ruxolitinib/placebo.

The purpose of this SAP is to provide details of the statistical analyses that have been outlined in the INCB 18424-369 Protocol.

The details of the analysis methodology of biomarkers and pharmacodynamics and results will appear in a separate report.

## 2. STUDY INFORMATION, OBJECTIVES, AND ENDPOINTS

### 2.1. Protocol and Case Report Form Version

This SAP is based on INCB 18424-369 Protocol Amendment 1 dated 02 JUN 2020 and CRFs approved on 30 SEP 2020. Unless superseded by an amendment, this SAP will be effective for all subsequent Protocol amendments and eCRF versions.

### 2.2. Study Objectives and Endpoints

Table 1 presents the objectives and endpoints.

**Table 1: Objectives and Endpoints**

Objectives	Endpoints
Primary	
To evaluate the 28-day mortality rate of ruxolitinib 5 mg BID + SoC therapy and ruxolitinib 15 mg BID + SoC therapy compared with placebo + SoC therapy in participants with COVID-19–associated ARDS who require mechanical ventilation.	Proportion of participants who have died due to any cause through Study Day 29.
Secondary	
To evaluate the efficacy of ruxolitinib 5 mg BID + SoC therapy and ruxolitinib 15 mg BID + SoC therapy compared with placebo + SoC therapy on in-hospital outcomes in participants with COVID-19–associated ARDS who require mechanical ventilation.	At Day 29, the number of ventilator-free days, ICU-free days, oxygen-free days, vasopressor-free days, and hospital-free days will be summarized by treatment group.
To evaluate the efficacy of ruxolitinib 5 mg BID + SoC therapy and ruxolitinib 15 mg BID + SoC therapy compared with placebo + SoC therapy using a 9-point ordinal scale at Study Days 15 and 29 in participants with COVID-19–associated ARDS who require mechanical ventilation.	Ordinal scale: 
 
• Percentage of participants with at least 2-point improvement in clinical status at Day 15 and at Day 29.
 
• Percentage of participants with at least 1-point improvement in clinical status at Day 15 and at Day 29.
 
• Time to improvement from baseline category to earliest 1-point improvement in the ordinal scale.
 
• Percentage of participants in each 9-point ordinal scale category at Day 29.
 
• Mean change in the 9-point ordinal scale from baseline to Days 15 and 29.
 

**Table 1: Objectives and Endpoints (Continued)**

Objectives	Endpoints
To evaluate the efficacy of ruxolitinib 5 mg BID + SoC therapy and ruxolitinib 15 mg BID + SoC therapy compared with placebo + SoC therapy on change from baseline SOFA score in participants with COVID-19–associated ARDS who require mechanical ventilation.	Change from baseline to Day 3, 5, 8, 11, 15, and 29 in SOFA score.
To evaluate the safety of ruxolitinib 5 mg BID + SoC therapy and ruxolitinib 15 mg BID + SoC therapy compared with placebo + SoC therapy in the treatment of participants with COVID-19–associated ARDS who require mechanical ventilation.	Number and proportion of participants with treatment-related side effects (as assessed by CTCAE v5.0) and SAEs; includes clinically significant changes in laboratory measures and vital signs.
Exploratory	
To evaluate the efficacy of ruxolitinib + SoC therapy compared with placebo + SoC therapy in proportion of participants requiring IL-6, IL-1, GM-CSF, or JAK-directed therapies.	Proportion of participants requiring treatments with IL-6, IL-6RA, IL-1RA, IL-1 beta, GM-CSF, BTK, or JAK directed therapies by Day 15 and by Day 29.
To evaluate ruxolitinib + SoC therapy compared with placebo + SoC therapy on change in inflammatory markers (when available).	Change from baseline to Day 15 and to Day 29 in the following clinical chemistry measurements: 
 
• Serum ferritin
 
• CRP
 
• D-dimer
 
• Procalcitonin
 
• IL-6
 

To evaluate ruxolitinib + SoC therapy compared with placebo + SoC therapy on change in COVID-19 virologic and serologic parameters.	Change from baseline to Day 15 and Day 29 in viral load and anti–SARS-CoV-2-antibody titer.

### 3. STUDY DESIGN

[figure not shown]
This is a randomized, double-blind, placebo-controlled, 29-day, multicenter study to assess the efficacy and safety of ruxolitinib 5 mg BID + SoC therapy and 15 mg BID + SoC therapy compared with placebo + SoC therapy in participants aged  $\geq 12$  years with COVID-19–associated ARDS who require mechanical ventilation (see Figure 1).

Participants aged  $\geq 12$  years with SARS-CoV-2 infection confirmed  $\leq 3$  weeks before randomization by any test with local regulatory approval, hospitalized with COVID-19–associated ARDS (demonstrated by chest x-ray or chest computerized tomography and  $\text{PaO}_2/\text{FiO}_2 \leq 300$  mmHg) who have been intubated and are receiving mechanical ventilation. Participants who are unlikely to survive for  $> 24$  hours after randomization (in the opinion of the treating investigator); who have active tuberculosis or active and uncontrolled bacterial, fungal, viral, or other infection (besides SARS-CoV-2); or who are currently receiving ECMO support will be excluded from the study.

The study will include the following:

- Screening period of 1 day.
- Study period of 29 days. Treatment with ruxolitinib 5 mg BID/placebo or ruxolitinib 15 mg BID/placebo will initially be administered for 14 days. If in the opinion of the treating investigator the benefit/risk is appropriate for the participant, then continued treatment up to 28 days permitted with approval from the sponsor medical monitor. Approval must be requested  $\geq 24$  hours before initiation of dosing on Day 15.
- AE follow-up assessment 28 ( $\pm 3$ ) days following the last dose of study treatment.

**Figure 1: Study Design**

- $\geq 12$  years
- Confirmed SARS-CoV-2 infection confirmed  $\leq 3$  weeks prior to randomization
- Patients with COVID-19–associated ARDS who require mechanical ventilation
- Lung imaging demonstrating bilateral or diffuse pulmonary infiltrates

a Not inclusive; see Protocol Section 6 for complete eligibility criteria.  
b Placebo arm will be randomized between a 5 mg BID (1 tablet/dose) and 15 mg BID (3 tablets/dose).

Eligible participants will be randomized after completing the screening period (Day -1) and having been confirmed eligible. Screening and randomization may occur on the same day. Participants will be assigned in a 2:2:1 ratio to receive ruxolitinib 5 mg BID, 15 mg BID, or matching-image placebo for an initial period of 14 days (refer to Protocol Section 7.1);

participants randomized to placebo will be randomized 1:1 to receive either matching placebo for 5 mg BID (1 tablet BID) or matching placebo for 15 mg BID (3 tablets BID). On Day 15, if in the opinion of the investigator the benefit/risk is appropriate, then continued treatment up to 28 days permitted with medical monitor approval. There is no crossover between treatment groups. Study treatment will be given in combination with SoC therapy according to the investigator's clinical judgment. Study treatment will be administered via an enteric feeding tube (refer to Protocol Section 7.1) while the participant is intubated. Randomization will be stratified by ARDS severity (severe [ $\text{PaO}_2/\text{FiO}_2 \leq 100$ ] vs mild/moderate [ $\text{PaO}_2/\text{FiO}_2 > 100$  and  $\leq 300$ ]) and investigative site.

### **3.1. Randomization**

Participants will be randomized 2:2:1 to receive ruxolitinib 5 mg BID, 15 mg BID, or matching-image placebo for an initial period of 14 days. Placebo participants will be randomized 1:1 to receive either the 5 mg BID image or the 15 mg BID image. Block randomization with stratification for ARDS severity (severe [ $\text{PaO}_2/\text{FiO}_2 \leq 100$ ] vs mild/moderate [ $\text{PaO}_2/\text{FiO}_2 > 100$  and  $\leq 300$ ]) and investigational site will be used.

### **3.2. Control of Type I Error**

The Type 1 error level for the primary endpoint is 1-sided 2.5%. A fixed sequence testing procedure will be used to test the 15 mg BID group against placebo first, and if that is significant, then the 5 mg BID group will be tested against placebo. If the test for the 15 mg BID group is not significant, the 5 mg BID group will not be tested.

If the null hypotheses are rejected for both ruxolitinib treatment groups when compared with placebo for the primary endpoint, then a statistical comparison will be performed between the 2 ruxolitinib groups.

No multiplicity adjustments will be applied to other endpoints. Secondary efficacy variables will be tested at a 0.05 level and will use a 2-sided test. All exploratory variables will use a 2-sided, 5% alpha with no adjustment for multiplicity.

### **3.3. Sample Size Considerations**

The primary endpoint of this study is the proportion of participants who die due to any cause through Study Day 29. The primary endpoint will be tested for each ruxolitinib treatment group using a logistic regression model including treatment (ruxolitinib vs placebo) and ARDS severity (severe [ $\text{PaO}_2/\text{FiO}_2 \leq 100$ ] vs mild/moderate [ $\text{PaO}_2/\text{FiO}_2 > 100$  and  $\leq 300$ ]) as fixed covariates and investigational site as a random (intercept) effect. For placebo randomized 2:2:1 (ruxolitinib 5 mg BID:ruxolitinib 15 mg BID:placebo) assuming a 40% mortality rate for ruxolitinib versus 60% for placebo, a sample size for a pairwise comparison of 100 placebo and 200 ruxolitinib participants (with 500 participants total) will achieve approximately 83% power to detect a statistically significant difference with a nominal 1-sided Type I error of 1.436968%.

Estimated power and Type I error for various scenarios, based on a simulation study of 1000 study replications, are provided in [Table 2](#).

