**Table 2: Simulation Estimates for Power and Type 1 Error for Various Mortality Rates**

Mortality Rates			Probability to Reject H 0 for		
PLB	5 mg BID	15 mg BID	5 mg BID	15 mg BID	Either RUX
60%	60%	60%	0.015	0.016	0.027
60%	60%	40%	0.012	0.873	0.873
60%	50%	40%	0.268	0.865	0.866
60%	40%	40%	0.868	0.872	0.940
60%	40%	30%	0.861	0.998	0.998

Note: For the simulation, investigational site was drawn from an integer uniform distribution (1, 2, ..., 10) and probability (ARDS severe) = 0.5, fitting a mixed logistic regression model with no direct effects for the ARDS severity or site.

Enrollment was halted and SAP Amendment 3 removed the interim analysis. The final analysis will be performed using all randomized participants enrolled at the time of SAP Amendment 3, which is 211 participants.

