### 7.2. Efficacy Hypotheses

The primary hypothesis is that ruxolitinib in combination with SoC will reduce 28-day mortality, as measured by odds ratio, compared with placebo in combination with SoC in participants with COVID-19–associated ARDS who require mechanical ventilation. The hypothesis of the study are as follows:

- $H_0$  (null hypothesis):  $\theta_{RUX05} = \theta_{RUX15} = \theta_{PLB}$
- $H_A$ (alternative hypothesis):  $\theta_{RUX15} < \theta_{PLB}$  OR ( $\theta_{RUX05} < \theta_{PLB}$  and  $\theta_{RUX15} < \theta_{PLB}$ )

The 5 mg BID hypothesis will only be tested if the 15 mg BID hypothesis is significant. In the event that both individual null hypotheses are rejected, then a test for a difference between the 5 mg BID and 15 mg BID treatment groups will be performed for the 28-day mortality endpoint. The hypothesis for this test is:

- $H_0$  (null hypothesis):  $\theta_{RUX05} = \theta_{RUX15}$
- $H_A$ (alternative hypothesis):  $\theta_{RUX15} \neq \theta_{RUX05}$

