### 7.3. Analysis of the Primary Efficacy Parameter

#### 7.3.1. Primary Efficacy Analysis

The primary endpoint, 28-day mortality, will be tested using a logistic regression mixed model including treatment group (specific ruxolitinib treatment group vs placebo) and ARDS severity (severe vs mild/moderate) as fixed covariates and investigational site as a random (intercept) effect. The estimation technique for the model fit will use the residual pseudo-likelihood with a subject-specific expansion ([SAS Institute 2013](#)) approach and will be implemented in the SAS GLIMMIX procedure. If the model is not estimable due to convergence issues, a fixed effects logistic regression will be performed instead, excluding investigational site from the model. The Wald test for the treatment regression coefficient will test the primary endpoint.

An estimate and 95% CI for the difference in proportions for 28-day mortality for the 2 treatment groups will be provided. The estimate will be based on the logistic regression model ([Ge et al 2011](#)) using an average of the difference between the 2 levels of the fixed factor (ARDS severity) weighted for the proportion of the study population within each of the 2 levels

of the fixed factor. The delta method will be used to derive the variance estimate, based on the functional form of the estimate  $\gamma^T g(\underline{b})$  using  $\gamma = (\gamma_1, \gamma_2)$  where

- $\gamma_1$  is the proportion of participants in the  $b_2 = 0$
- $\gamma_2$  is the proportion of participants in the  $b_2 = 1$

$\underline{b}$  is the vector of the logistic regression coefficients, and

$$g(\underline{b}) = \frac{1/1 + \exp(\underline{\gamma}^T \underline{b}_0 - b_1) - 1/1 + \exp(\underline{\gamma}^T \underline{b}_0)}{1/1 + \exp(\underline{\gamma}^T \underline{b}_0 - b_1 - b_2) - 1/1 + \exp(\underline{\gamma}^T \underline{b}_0 - b_2)} .$$

Point estimates and 95% CIs will also be provided for the model-based mortality rates using the delta method.

Participants who are lost to follow-up before Day 29 will not be evaluable for this endpoint. As the participants begin the study intubated, those who remain hospitalized are unlikely to be lost to follow-up, but reasonable efforts will be made to track down missing participants.

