## 10. INTERIM ANALYSES

Per SAP Amendment 3, no interim analysis will be performed.

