### 11.1. Changes to Protocol-Defined Analyses

#### 11.1.1. Original to Amendment 1

- The analysis for time to improvement from baseline category to earliest 1-point improvement in the ordinal scale was restated as time to improvement from baseline category to earliest improvement of any kind.
- After FDA feedback, the initial plan for treatment groups continued beyond rejection of their specific null hypothesis at the efficacy interim analysis where final reported p-values would be based on the highest level of significance achieved, either at the interim or final analysis, was modified to report p-values from the final analysis at final reporting.
- Gender was removed from analyses of the primary and secondary endpoints and added as a sensitivity analysis for the primary endpoint.

#### 11.1.2. Amendment 1 to Amendment 2

- The weekly overall survival futility analysis was replaced by a conditional power analysis to occur after approximately every 50 participants enrolled have at least 2 weeks of follow-up.
- The reference level of ARDS severity was changed to be mild/moderate instead of severe.

#### 11.1.3. Amendment 2 to Amendment 3

- Section 3.2, Section 3.3, Section 5.1, Section 7.3.1, Section 7.3.3, Section 10, Appendix A – The interim analysis and conditional power analysis were removed. The only remaining analysis will be the final analysis.
- Section 3.2, Section 5.3.3, Section 5.3.5, Section 7.2, Section 7.5.1, Section 7.5.2, Section 7.5.3, Appendix A – The alpha control strategy for the primary efficacy analysis was changed. The definition of the PP population was modified, and the PD-evaluable population was removed. Any planned analyses that previously used the PD-evaluable population will use the safety population instead.

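### SAP 3.3 still states the power and alpha of the dropped 500-participant Dunnett design; the 211-participant fixed sequence has about 55-58% power for 15 mg, not 83%

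*SAP*

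**What the plan says.** The rule now in force is in SAP 3.2: "The Type 1 error level for the primary endpoint is 1-sided 2.5%. A fixed sequence testing procedure will be used", with 15 mg tested first. The gate is explicit: "If the test for the 15 mg BID group is not significant, the 5 mg BID group will not be tested". SAP 7.2 repeats it: "The 5 mg BID hypothesis will only be tested if the 15 mg BID hypothesis is significant". SAP 10 adds: "Per SAP Amendment 3, no interim analysis will be performed". On size, the text under Table 2 says that enrollment was halted and that "The final analysis will be performed using all randomized participants enrolled at the time of SAP Amendment 3, which is 211 participants".

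SAP 3.3 nevertheless keeps the planning statement that 100 placebo and 200 ruxolitinib participants (500 in total), at 60% versus 40% mortality, "will achieve approximately 83% power to detect a statistically significant difference with a nominal 1-sided Type I error of 1.436968" percent. Protocol 12.1 shows where that alpha comes from: it is the Dunnett-adjusted level for two comparisons with correlation 2/3. SAP Table 2 has the same numbers as Protocol Table 8, which was built for the Dunnett design.

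The change log in SAP 11.1.3 records that "The alpha control strategy for the primary efficacy analysis was changed" and lists the sections affected. Section 3.3 is not among them. It is listed only for removal of the interim and conditional power analyses.

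**The concern.** The SAP's only power statement for the primary endpoint describes an analysis that will not be done. Two adjacent sections attach different 1-sided levels, 2.5% and 1.436968%, to the primary comparison.

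Table 2 also conflicts with the gate, whatever the sample size. In a sequence that starts with 15 mg, rejecting at least one hypothesis is the same event as rejecting 15 mg. The *Either RUX* column must therefore equal the 15 mg column, and the 5 mg column must be the probability that both tests reject. Table 2 has neither property.

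What is at stake is interpretation. A reader of a non-significant result who relies on 83% would take it as much stronger evidence against a 20-point mortality reduction than it is. A failed 15 mg test also leaves 5 mg untested.

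**Working it through.** **Inputs.** Mortality of 60% placebo and 40% ruxolitinib, 100 versus 200, and alpha 0.01436968 (SAP 3.3). Alpha 0.025 and the fixed sequence (SAP 3.2). Allocation 2:2:1 (SAP 3.1). Total 211 (text under Table 2). Wald test (SAP 7.3.1). The arm sizes at 211 are not in the documents; 42 placebo, 84 at 5 mg and 85 at 15 mg are assumed. No dropout rate is given; zero is assumed first. The calculations use unadjusted two-group tests, not the mixed model with site and severity.

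**Formulas.** With difference d = 0.20, pooled rate p, SE0 = sqrt[p(1-p)(1/n1 + 1/n2)] and SE1 = sqrt[0.6×0.4/n1 + 0.4×0.6/n2]:

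- Unpooled power = Φ(d/SE1 − z)
- Pooled power = Φ((d − z·SE0)/SE1)
- Continuity-corrected power = Φ((d − c − z·SE0)/SE1), with c = ½(1/n1 + 1/n2)

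**Step 1: the stated design reproduces.** For 100 versus 200 at 0.01436968: z = 2.187, SE0 = 0.0611, SE1 = 0.0600, c = 0.0075.

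- Continuity-corrected: Φ((0.20 − 0.0075 − 0.1336)/0.0600) = Φ(0.981) = 0.837. Exact Fisher gives 0.832. Either is consistent with the stated 83%.
- Pooled: Φ(1.106) = 0.866. Exact enumeration of the log-odds-ratio Wald test gives 0.869, in line with the 0.861-0.873 in Table 2 for an arm at 40%.
- Exact Wald for both arms at 40%, sharing the placebo group: 0.869 each and 0.937 for either. Table 2 has 0.868, 0.872 and 0.940.

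The 83% and Table 2 are therefore correct for ungated Dunnett testing with 500 participants.

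**Step 2: 15 mg under the current design.** For 42 versus 85 at 0.025: z = 1.960, SE0 = 0.0941, SE1 = 0.0924, c = 0.0178.

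- Unpooled: Φ(0.2000/0.0924 − 1.960) = Φ(0.205) = 0.581
- Pooled: Φ((0.2000 − 0.1844)/0.0924) = Φ(0.169) = 0.567
- Log-odds-ratio Wald formula: Φ(0.811/0.385 − 1.960) = Φ(0.146) = 0.558
- Exact Wald: 0.551
- Continuity-corrected: Φ(−0.024) = 0.491

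**Step 3: the gated probabilities.** Exact Wald enumeration, conditioning on the shared placebo count, for 42/84/85 at 0.025:

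| Placebo / 5 mg / 15 mg mortality | 15 mg, Table 2 | 15 mg, current design | 5 mg, Table 2 (ungated) | 5 mg through gate, current design |
|---|---|---|---|---|
| 60/60/60 | 0.016 | 0.023 | 0.015 | 0.007 |
| 60/60/40 | 0.873 | 0.551 | 0.012 | 0.023 |
| 60/50/40 | 0.865 | 0.551 | 0.268 | 0.167 |
| 60/40/40 | 0.872 | 0.551 | 0.868 | 0.427 |
| 60/40/30 | 0.998 | 0.900 | 0.861 | 0.558 |

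A simulation of 400,000 trials at 60/40/40 gave the same 0.551 and 0.427.

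**Step 4: the *Either RUX* column.** Against the 15 mg column, Table 2 shows 0.940 versus 0.872 (60/40/40) and 0.027 versus 0.016 (null). The other three rows agree within 0.001. The two larger gaps cannot occur under the gate at any sample size.

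**Step 5: sensitivity at 60/40/40 (15 mg; 5 mg through the gate).**

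- 38/86/87: 0.535; 0.409
- 42/85/84: 0.569; 0.427
- 43/84/84: 0.579; 0.449
- 46/82/83: 0.586; 0.452
- 10% non-evaluable, 38/76/76: 0.541; 0.408. This case matters because, under SAP 7.3.1, "Participants who are lost to follow-up before Day 29 will not be evaluable for this endpoint".

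**Step 6: the cause.** The same fixed sequence at 0.025 with 100/200/200 gives 0.906 for 15 mg and 0.850 for 5 mg. The loss comes from the sample size; the less strict alpha works in the other direction.

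**The case against.** The strongest reply is that no stated figure is miscalculated. SAP 3.3 ties its 83% to 500 participants at 1.436968%, and that reproduces. The halt and the 211 are disclosed in the same section, so a careful reader would not take 83% as the power of the final analysis. The operative alpha is clear from Sections 3.2 and 7.2, and no analyst would test at 1.436968%. Keeping the planning rationale is legitimate, enrollment has stopped, and recomputed power cannot alter the trial. The range of 55-58% is also not the direct successor to 83%, which matches a continuity-corrected or Fisher calculation.

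Much of this stands. The figures are right for the old design, and no decision rule is affected. The like-for-like successor to 83% is about 0.49 to 0.50; 55-58% is comparable with the 87% in Table 2, because both use a Wald or z-test. The omission in the change log supports this reading but does not prove an oversight.

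The main point remains. The sentence on the halt mentions the smaller total and the removed interim. It does not say that the power, the alpha or Table 2 no longer apply, and it gives nothing in their place. The verb is still in the future tense, directly after a section that sets a different alpha. The disclosure of 211 also does not reconcile an ungated table with a gated procedure.

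**Conclusion.** The concern holds. As written, SAP 3.3 and Table 2 give operating characteristics that the defined analysis does not have. At the SAP's own planning effect, 15 mg power is about 0.55 (exact Wald) to 0.58 (unpooled formula), so a 20-point mortality reduction would be missed about 42-45% of the time. The probability of claiming 5 mg is about 0.43 if both arms are at 40%.

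These values assume a 42/84/85 split, no dropout and an unadjusted test. Moving the placebo arm between 38 and 46 gives 0.54-0.59 for 15 mg and 0.41-0.45 for 5 mg; 10% non-evaluable gives 0.54 and 0.41. A continuity-corrected calculation gives 0.49. None of these is close to 83%. The conflict between Table 2 and the gate needs none of these assumptions. This should be fixed, although no p-value or testing rule changes.

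**What to change.** In SAP 3.3:

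1. Label the 500-participant statement and Table 2 as historical planning values for the superseded Dunnett design.
2. Remove 1.436968% as a property of the final analysis, leaving 1-sided 2.5% as the only level for the primary comparison.
3. Name the method behind the 83%, since it is lower than the 0.868-0.873 simulated for 60% versus 40% with the other arm at 40% or 60%.
4. Replace or supplement Table 2 with operating characteristics for the actual arm sizes under the 15 mg then 5 mg sequence. Gate the 5 mg column on 15 mg, omit a separate *Either RUX* column, and state the resulting power for each scenario.

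The cost is SAP wording and one re-run of the existing simulation. It needs no participants and changes no test. The stated power becomes less favourable.
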